### **CB-839 and Capecitabine, Cycle 2 and beyond, Day 1**

All assessments may be performed +/- one day

- Physical examination
- Weight
- Vital signs including temperature, heart rate, blood pressure and respiratory rate
- Concomitant medications including over the counter medications and supplements
- ECOG performance status
- Symptom/adverse event assessment
- Laboratory studies
  - Complete blood count (CBC) with differential
  - Comprehensive metabolic panel
  - Calculated creatinine clearance if creatinine and/or BUN are abnormal
  - CEA (carcinoembryonic antigen) blood test
- Administration of CB-839 by mouth twice daily for a 21 day treatment cycle
- Administration of capecitabine by mouth twice daily for first 14 days of 21 day cycle

### **CB-839 and Capecitabine, Cycle 3, sometime between days 15-21 of treatment cycle**

- CT of the chest, abdomen and pelvis for restaging evaluation

**Subsequent CT imaging of the chest, abdomen and pelvis should be performed on an every 9 week basis +/- one week for as long as patient is receiving study treatment**

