Sample Size	Phase I: 9-24 patients Phase II: 18-40 patients Males and females permitted
Disease sites/ Conditions	Phase I: all solid tumors Phase II: metastatic colorectal cancer, PIK3CA mutant
Interventions	Phase I: Patients will receive CB-839 orally twice daily for 21 days (continuous administration) and capecitabine orally twice daily for 14/21 days. Dosing of CB-839 and capecitabine will occur according to the aforementioned dosing table. Day 15 through CB-839 pharmacokinetics will be assessed. Patients will undergo a disease assessment with CT imaging of the chest, abdomen and pelvis following 3 cycles (9 weeks) of treatment.
	Phase II: Patients will be treated with CB-839 800 mg by mouth twice daily for 21 days (continuous dosing) as well as capecitabine 1000 mg/m  by mouth twice daily for 14/21 days as was determined during the phase I portion of the study. Pre-treatment and post-10-15 day treatment blood samples will be obtained for assessment of glutaminase activity (to be obtained the same day as the post-treatment biopsy). Day 15 blood samples will also be archived for as needed assessment of CB-839 pharmacokinetics. Baseline tissue biopsies and a day 10-15 tissue biopsy will be obtained to assess tissue glutaminase activity and nucleotide levels as well as for whole exome sequencing, RNA seq and for the production of organoids. Patients will be assessed with CT scans of the chest, abdomen and pelvis every 3 cycles (9 weeks). Treatment will continue until disease progression, until unacceptable toxicity develops or per patient/physician preference.

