## **7.0 DOSE DELAYS/DOSE MODIFICATIONS**

Once a patient undergoes a dose modification, neither CB-839 nor capecitabine may be re-escalated in that patient.

Dose reductions may be implemented for either one agent or both agents depending on the treating physician's assessment of causality.

Patients requiring > 2 dose modification will be taken off protocol therapy.

Patients must receive at least 75% of the total assigned CB-839 and capecitabine doses in order to be evaluable for a DLT in the phase I portion of the study. Missed doses must be for reasons other

than toxicity.

For patients in the phase I portion of the study, dose reductions of CB-839 and capecitabine will be permitted during the first cycle (21 days) only if a patient experiences a toxicity that results in a DLT. If a patient experiences a DLT, treatment continuation at a lower dose of CB-839 and/or capecitabine will be permitted as long as the toxicity has returned to  $\leq$  Grade 1 or baseline within 14 days. Upon recovery, patients may restart at one CB-839/capecitabine dose level lower. Patients who do not recover within 14 days will not be eligible for resumption of treatment with CB-839 or capecitabine.

After cycle 1, dose reductions or interruptions for adverse events may take place at any time at the discretion of the Principal Investigator. Dose interruptions for grade 2 non-hematologic toxicity for up to 5 days can be implemented at the discretion of the treating physician to manage clinically significant toxicity. No dose reduction is required when resuming treatment. Dose interruptions of  $>$  5 days should be discussed with the PI. Patients whose dose is interrupted for  $>$  21 days for any reason must be withdrawn from the study unless prior approval from the PI has been obtained for study continuation.

Adequate medical management for reversible symptoms using supportive medications must be used prior to making a dose modification for these symptoms.

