## 11.4 Calendar—Phase II Component

Study Days	Pre-Study a	Pre-treatment	CB-839 and cape, C1D1 b	CB-839 and cape, C1D8	CB-839 and cape, C1D15	Cycle 2 and beyond, Day 1	Cycle 3, Day 14-21	Every 9 weeks	30 Day Follow-Up
REQUIRED ASSESSMENTS									
Informed Consent	X								
Demographics	X								
Medical History	X								
Height	X								
Weight	X		X			X			X
Vitals	X		X			X			X
Physical Examination	X		X			X			X
Concomitant Med Assessment	X		X			X			
ECOG PS	X		X			X			X
Symptom/Adverse Event Assessment	X		X	X	X	X			X
CBC with diff d	X		X	X	X	X			X
Serum comprehensive panel d	X		X	X	X	X			X
CEA (carcinoembryonic antigen) blood test	X					X			
Pregnancy test (if applicable)	X								
DISEASE ASSESSMENT									
Tumor measurements		Tumor assessments are performed at baseline and every 9 weeks. Documentation (radiologic) must be provided for patient removed from study for progressive disease.							
CT chest, abdomen and pelvis	X						X	X g	
MISC ITEMS									
Tumor biopsy		X c			X e				
TREATMENT									
CB-839			X h			X			
Capecitabine			X h			X			
CORRELATIVE STUDIES									
Pharmacodynamic studies		X c			X c				
Pharmacokinetics (CB-839)					X f				

a All evaluations must be completed  $\leq$  21 days prior to administration of protocol therapy.

b Cycle 1, Day 1 assessments do not need to be repeated if done within 7 days of initiation of treatment.

c Tumor biopsy may be done up to 14 days prior to initiation of treatment. Please allow 28 days washout from prior systemic therapy prior to pre-treatment biopsy. Platelet glutaminase assay should be drawn the same day as performance of the tissue biopsy. Glutaminase activity will only be assessed on the post-treatment blood and tissue specimens.

d CBC with differential and comprehensive panel for day 1 of the treatment cycle may be drawn up to 24 hours prior to treatment. Serum comprehensive panel should include sodium, potassium, chloride, bicarbonate, BUN, creatinine, glucose, AST, ALT, alk phos, total protein, albumin, total bilirubin, direct bilirubin, magnesium and phosphorus.

e Post-treatment tissue biopsy may be performed day 10-15. Platelet glutaminase assay should be drawn the same day as performance of the tissue biopsy.

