f Pharmacokinetic sample should be drawn just prior to the administration of the morning dose of CB-839 and capecitabine.

g Restaging CT scans may be performed +/- 7 days at all timepoints beyond the cycle 3 evaluation.

h Treatment starts this day. CB-839 is to be taken twice daily continuously (21/21 days) and capecitabine is to be taken twice daily for 14/21 days).

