## **12.0 MEASUREMENT OF EFFECT**

Although response is not the primary endpoint of the phase I portion of this trial, patients will be assessed by standard criteria. Response rate is the primary endpoint for the phase II portion of the trial. For the purposes of this study, patients should be re-evaluated every 9 weeks in addition to undergoing a baseline scan.

Response and progression will be evaluated in this study using the new international criteria proposed by the revised Response Evaluation Criteria in Solid Tumors (RECIST) guideline (version 1.1) (23). Changes in the largest diameter (unidimensional measurement) of the tumor lesions and the shortest diameter in the case of malignant lymph nodes are used in the RECIST criteria.

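### The first phase II restaging CT is placed by treatment cycle and later CTs by weeks with no stated day 0, so a dose hold before the first CT can move the scans that decide 6-month PFS

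*Combined protocol and SAP*

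**What the plan says.** The phase II schedule is described in two units.

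- **By cycle.** Section 11.2.2 places the first restaging CT in "Cycle 3, sometime between days 15-21 of treatment cycle". The section 11.4 calendar heads the column "Cycle 3, Day 14-21", a start one day earlier. The Protocol Summary says "Patients will be assessed with CT scans of the chest, abdomen and pelvis every 3 cycles (9 weeks"), treating 3 cycles and 9 weeks as the same thing. The phase II design section (3.2) and the phase II schema also equate the two.
- **By weeks.** For CTs after the first, section 11.2.2 says they "should be performed on an every 9 week basis +/- one week for as long as patient is receiving study treatment". The calendar says "Tumor assessments are performed at baseline and every 9 weeks", with the footnote "Restaging CT scans may be performed +/- 7 days at all timepoints beyond the cycle 3 evaluation". Section 12.0 says "patients should be re-evaluated every 9 weeks in addition to undergoing a baseline scan".

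No section says whether the 9 weeks run from first dose or from the previous scan, whether a hold stops the cycle-day count, or whether scans stay on schedule during a hold.

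Holds are foreseen. Sections 7.1.2, 7.2.1 and 7.2.2 interrupt drug until toxicity resolves or counts recover. Section 7.0 sets the outer limit: a patient interrupted for more than "21 days for any reason must be withdrawn from the study unless prior approval from the PI has been obtained".

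The primary endpoint in section 14.2 is the PFS rate at 6 months, 18% under the null against a target of 36%. Section 14.1.1 determines PFS by clinical assessment and RECIST. Section 12.5 counts PFS from the start of treatment.

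**The concern.** PFS is measured from start of treatment, but the first scan that can document progression is placed by a cycle count that toxicity may stretch. Two patients with the same tumour course could then have different progression dates, and a different status at 6 months, because one had a drug hold before the first CT. Sites could also read the text differently and all comply: one scans at week 9 during a hold, another waits for cycle 3 day 15.

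The trial has one arm and is judged against a fixed 18%. There is no control group in which the same shift in timing would occur, so comparability with the null depends on a schedule that does not vary with tolerability.

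**Working it through.** **1. The plan's own equivalence.** 3 cycles x 21 days = 63 days = 9 weeks, so the cycle and week wordings agree with no delay. Cycle 3 days 15-21 are study days 42 + 15 = 57 to 42 + 21 = 63, that is (57 - 1)/7 = 8.0 to (63 - 1)/7 = 8.9 weeks after first dose. The calendar's day 14 is study day 56.

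**2. Scan times with a delay of D weeks before the first CT.** This assumes that the hold stops the cycle count and that each later interval runs 9 +/- 1 weeks from the previous scan.

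| D | Nominal weeks | CT 1 | CT 2 | CT 3 |
|---|---|---|---|---|
| 0 | 9, 18, 27 | 8.0-8.9 | 16.0-18.9 | 24.0-28.9 |
| 3 | 12, 21, 30 | 11.0-11.9 | 19.0-21.9 | 27.0-31.9 |

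With no delay the third scan may fall before or after 26 weeks. With a 3-week delay it always falls after. A hold that begins after the first CT moves nothing under section 11.2.2; it moves scans only under the Protocol Summary's every-3-cycles wording.

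**3. Effect on one patient's 6-month status.** Assumptions: exponential PFS, true 6-month rate 18% (the null in section 14.2), 6 months = 26.09 weeks, progression found only at nominal scan times.

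Hazard = -ln(0.18)/26.09 = 0.0657 per week, and S(t) = exp(-0.0657t).

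| Status rule | No delay | 3-week delay | Difference |
|---|---|---|---|
| No documented progression by 6 months (last scan before 26 weeks) | S(18) = 30.6% | S(21) = 25.2% | 5.4 points |
| Read at the third scan | S(27) = 17.0% | S(30) = 13.9% | 3.1 points |

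A 2-week delay gives S(20) = 26.9% and S(29) = 14.9%, differences of 3.7 and 2.1 points. At the 36% target the first rule gives 49.4% with no delay and 43.9% with a 3-week delay.

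**4. Effect on documented PFS time.** The mean documented time with scans every 9 weeks is 9/(1 - S(9)) = 20.2 weeks. With the first scan at week 12 and 9-week intervals after it, the mean is 12 + S(12) x 20.2 = 21.2 weeks. The true mean is 1/0.0657 = 15.2 weeks. The delay adds about 1 week in a delayed patient.

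**5. Trial level.** The shift is the share of delayed patients times the difference in step 3. The documents give no share, so these are assumptions for a 3-week delay.

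| Share delayed | By-6-months rule | Third-scan rule |
|---|---|---|
| 10% | 0.5 points | 0.3 points |
| 20% | 1.1 points | 0.6 points |
| 40% | 2.2 points | 1.2 points |
| 100% (ceiling) | 5.4 points | 3.1 points |

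**6. Direction.** Under the first rule a delay brings the measured rate closer to the true 18% (30.6 to 25.2). Under the second it moves it further away (17.0 to 13.9). The plan does not state the rule.

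**The case against.** The case on the other side has five parts.

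- **Most of the schedule is already in weeks.** A reader might infer from the Protocol Summary that every phase II CT is tied to the cycle. The documents do not support that. Section 11.2.2 puts only the first CT by cycle and the rest on a 9-week basis, and sections 11.4 and 12.0 agree with the latter. This stands. What remains is the first scan and whatever is counted from it.
- **That a hold stops the cycle count is an inference.** Section 6.2 says missed doses are not made up and the next dose is taken at its usual time, which fits a clock that keeps running. Reductions may apply to one agent only (section 7.0). This stands too, but the text is silent either way, and that silence is the gap.
- **Long holds are restricted.** Section 7.0 asks for discussion with the PI beyond 5 days. Section 7.1.2 withdraws patients whose grade 3 or 4 symptoms persist beyond 14 days. Section 3.3.2 replaces a patient who takes under 75% of planned doses of each agent before the 9-week assessment. Counted against 63 calendar days, a 21-day hold leaves 42/63 = 67% of CB-839 doses, so that patient would be replaced. If doses are merely postponed, the rule may not apply. A 3-week delay is therefore near the upper end, and a schedule of weeks 15, 24 and 33 would need two such holds before the first CT. Nothing in the documents suggests that this is common.
- **Scans are not the only source of events.** Clinical assessment and death also count, so the differences in the working are upper values.
- **The 9-week grid matters more.** With no delay, the by-6-months rule already reads 30.6% for a true 18%, a gap of 12.6 points. That is correct, and it is a separate question. Defining the status rule would not remove the dependence of scan dates on holds.

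**Conclusion.** The point holds in a limited form. The first phase II restaging CT is set by cycle, later CTs by weeks with no stated day 0, and the text allows a hold before the first CT to move that scan and any scan counted from it. For a patient with a 3-week delay, the chance of being counted as a 6-month success changes by 5.4 or 3.1 points according to the status rule. For the trial, the change is about 1.1 or 0.6 points if 20% of patients are delayed. These figures rest on exponential PFS, a true rate of 18%, detection only at scans and a cycle count that stops during holds.

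A reader might take the per-patient differences as the bias in the trial's result. The documents do not support that: it would require every patient to be delayed, and the direction relative to the true rate depends on a rule the plan does not state. Nor is there a between-arm bias in a single-arm trial. The effect is probably small, but it comes from toxicity, it touches the primary endpoint, and it can be removed at almost no cost, so the change is worth making.

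**What to change.** In section 11.2.2, the section 11.4 calendar, section 3.2 (phase II design) and the Protocol Summary, schedule restaging CTs at weeks 9, 18, 27 and so on from cycle 1 day 1, each +/- 1 week, regardless of dose holds, delays or cycle number. Remove the cycle 3 and every-3-cycles anchors, and align the phase II schema. This also removes the day 14/15 mismatch between sections 11.2.2 and 11.4.

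The cost is a wording amendment. The scan interval is unchanged, and patients without a delay see essentially no difference. In delayed patients some scans will fall on a different day of the treatment cycle, which may mean a separate visit.

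This change does not settle which scan decides 6-month status. The nominal week 27 scan falls after 26 weeks, so the plan still needs a stated rule or window for the primary endpoint.

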### 11.3 Calendar—Phase I Component

Study Days	Pre-Study a	CB-839 and cape, C1D1 b	CB-839 and cape, C1D8	CB-839 and cape, C1D15	Cycle 2 and beyond, Day 1	Cycle 3, Day 14-21	Every 9 weeks	30 Day Follow-Up
REQUIRED ASSESSMENTS								
Informed Consent	X							
Demographics	X							
Medical History	X							
Height	X							
Weight	X	X			X			X
Vitals	X	X			X			X
Physical Examination	X	X			X			X
Concomitant Med Assessment	X	X			X			
ECOG PS	X	X			X			X
Symptom/Adverse Event Assessment	X	X	X	X	X			X
CBC with diff c	X	X	X	X	X			X
Serum comprehensive panel d	X	X	X	X	X			X
Pregnancy test (if applicable)	X							
DISEASE ASSESSMENT								
CT chest, abdomen and pelvis	X					X	X e	
		Tumor assessments are performed at baseline and every 9 weeks. Documentation (radiologic) must be provided for patient removed from study for progressive disease						
TREATMENT								
CB-839		X g			X			
Capecitabine		X g			X			
CORRELATIVE STUDIES								
Pharmacokinetics (CB-839)				X d				

aAll evaluations must be completed  $\leq$  21 days prior to administration of protocol therapy.

bCycle 1, Day 1 assessments do not need to be repeated if done within 7 days of initiation of treatment.

cCBC with differential and comprehensive panel for day 1 of the treatment cycle may be drawn up to 24 hours prior to treatment.

d Pharmacokinetic sample should be drawn just prior to the administration of the morning dose of CB-839 and capecitabine.

eRestaging CT scans may be performed +/- 7 days at all timepoints beyond the cycle 3 evaluation.

f Serum comprehensive panel should include sodium, potassium, chloride, bicarbonate, BUN, creatinine, glucose, AST, ALT, alk phos, total protein, albumin, total bilirubin, direct bilirubin, magnesium and phosphorus.

gTreatment starts this day. CB-839 is to be taken twice daily continuously (21/21 days) and capecitabine is to be taken twice daily for 14/21 days.

## 11.4 Calendar—Phase II Component

Study Days	Pre-Study a	Pre-treatment	CB-839 and cape, C1D1 b	CB-839 and cape, C1D8	CB-839 and cape, C1D15	Cycle 2 and beyond, Day 1	Cycle 3, Day 14-21	Every 9 weeks	30 Day Follow-Up
REQUIRED ASSESSMENTS									
Informed Consent	X								
Demographics	X								
Medical History	X								
Height	X								
Weight	X		X			X			X
Vitals	X		X			X			X
Physical Examination	X		X			X			X
Concomitant Med Assessment	X		X			X			
ECOG PS	X		X			X			X
Symptom/Adverse Event Assessment	X		X	X	X	X			X
CBC with diff d	X		X	X	X	X			X
Serum comprehensive panel d	X		X	X	X	X			X
CEA (carcinoembryonic antigen) blood test	X					X			
Pregnancy test (if applicable)	X								
DISEASE ASSESSMENT									
Tumor measurements		Tumor assessments are performed at baseline and every 9 weeks. Documentation (radiologic) must be provided for patient removed from study for progressive disease.							
CT chest, abdomen and pelvis	X						X	X g	
MISC ITEMS									
Tumor biopsy		X c			X e				
TREATMENT									
CB-839			X h			X			
Capecitabine			X h			X			
CORRELATIVE STUDIES									
Pharmacodynamic studies		X c			X c				
Pharmacokinetics (CB-839)					X f				

a All evaluations must be completed  $\leq$  21 days prior to administration of protocol therapy.

b Cycle 1, Day 1 assessments do not need to be repeated if done within 7 days of initiation of treatment.

c Tumor biopsy may be done up to 14 days prior to initiation of treatment. Please allow 28 days washout from prior systemic therapy prior to pre-treatment biopsy. Platelet glutaminase assay should be drawn the same day as performance of the tissue biopsy. Glutaminase activity will only be assessed on the post-treatment blood and tissue specimens.

d CBC with differential and comprehensive panel for day 1 of the treatment cycle may be drawn up to 24 hours prior to treatment. Serum comprehensive panel should include sodium, potassium, chloride, bicarbonate, BUN, creatinine, glucose, AST, ALT, alk phos, total protein, albumin, total bilirubin, direct bilirubin, magnesium and phosphorus.

e Post-treatment tissue biopsy may be performed day 10-15. Platelet glutaminase assay should be drawn the same day as performance of the tissue biopsy.

f Pharmacokinetic sample should be drawn just prior to the administration of the morning dose of CB-839 and capecitabine.

g Restaging CT scans may be performed +/- 7 days at all timepoints beyond the cycle 3 evaluation.

h Treatment starts this day. CB-839 is to be taken twice daily continuously (21/21 days) and capecitabine is to be taken twice daily for 14/21 days).

## **12.0 MEASUREMENT OF EFFECT**

Although response is not the primary endpoint of the phase I portion of this trial, patients will be assessed by standard criteria. Response rate is the primary endpoint for the phase II portion of the trial. For the purposes of this study, patients should be re-evaluated every 9 weeks in addition to undergoing a baseline scan.

Response and progression will be evaluated in this study using the new international criteria proposed by the revised Response Evaluation Criteria in Solid Tumors (RECIST) guideline (version 1.1) (23). Changes in the largest diameter (unidimensional measurement) of the tumor lesions and the shortest diameter in the case of malignant lymph nodes are used in the RECIST criteria.

### **12.1 Definitions**

Evaluable for toxicity: All patients who receive at least one dose of study drug (either CB-839 or capecitabine) will be included in the analysis of safety regardless of the duration of treatment.

Evaluable for objective response: Only those patients who have measurable disease present at baseline, have received at least one cycle of therapy, and have had their disease re-evaluated will be considered evaluable for response. These patients will have their response classified according to the definitions stated below. **Note:** Patients who exhibit objective disease progression prior to the end of cycle 1 will also be considered evaluable.

Evaluable Non-Target Disease Response: Patients who have lesions present at baseline that are evaluable, but do not meet the definitions of measurable disease, have received at least one cycle of therapy, and have had their disease re-evaluated will be considered evaluable for non-target disease. The response assessment is based on the presence, absence, or unequivocal progression of the lesions.

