### **3.3 Replacement of Patients**

3.3.1 Phase I: If a patient is withdrawn from the study for any reason other than a dose limiting toxicity prior to completing the first 21 days of combination therapy with CB-839 and capecitabine, a replacement patient will be enrolled and will be assigned to the same dose level.

Unless the patient has had their study drug held for an adverse event that may herald a DLT, if a patient does not take at least 75% of the planned doses of each of the two agents (CB-839 and capecitabine), the patient will be replaced because he/she has not taken enough drug to confirm safety at that dose level.

3.3.2 Phase II: If a patient does not take at least 75% of the planned doses of each of the two agents (CB-839 and capecitabine) prior to the first disease assessment (9 weeks), the patient will be replaced because he/she has not taken enough drug to assess efficacy.

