### For Patients with Measureable Disease (e.g. Target Disease)

Target Lesions	Non-Target Lesions	New Lesions*	Best Overall Response	Remarks
CR	CR	No	CR	
CR	Non-CR/Non-PD***	No	PR	
CR	Not evaluated	No	PR	
PR	Non-PD***/not evaluated	No	PR	
SD	Non-PD***/not evaluated	No	SD	Documented at least once $\geq 8$ wks. from study entry
PD	Any	Yes or No	PD	No prior SD, PR or CR
Any	PD**	Yes or No	PD***	
Any	Any	Yes	PD	

\* See RECIST 1.1 manuscript for further details on what is evidence of a new lesion.

\*\* In exceptional circumstances, unequivocal progression in non-target lesions may be accepted as disease progression.

\*\*\*PD in non-target lesions should not normally trump target lesion status. It must be representative of overall disease status change, not a single lesion increase. Please refer to the Evaluation of Non-Target Lesions – Progressive Disease (Section 12.2) for further

explanation.

**NOTE:** Patients with a global deterioration of health status requiring discontinuation of treatment without objective evidence of disease progression at that time should be reported as “*symptomatic deterioration*.” Every effort should be made to document the objective progression even after discontinuation of treatment.

Duration of overall response: The duration of overall response is measured from the time measurement criteria are met for CR or PR (whichever is first recorded) until the first date that recurrent or progressive disease is objectively documented (taking as reference for progressive disease the smallest measurements recorded since the treatment started). The duration of overall CR is measured from the time measurement criteria are first met for CR until the first date that progressive disease is objectively documented.

Duration of stable disease: Stable disease is measured from the start of the treatment until the criteria for progression are met, taking as reference the smallest measurements recorded since the treatment started, including the baseline measurements.

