#### 14.1.2 Definition of Secondary Endpoints

Phase I: Dose-limiting toxicities as assessed by CTCAE version 4 of combination CB-839 and capecitabine in patients with advanced solid tumors with no remaining treatment options or patients for whom single agent capecitabine is an acceptable therapy.

Phase I: Response rate as assessed by RECIST criteria of combination CB-839 and capecitabine chemotherapy in patients with advanced solid tumors with no remaining treatment options or patients for whom single agent capecitabine is an acceptable therapy.

Phase II: Response rate as assessed by RECIST criteria of combination CB-839 and capecitabine chemotherapy in patients with metastatic PIK3CA mutant colorectal cancer who are refractory to fluoropyrimidine based therapy.

Phase II: Overall survival of patients with metastatic PIK3CA mutant colorectal cancer who are refractory to fluoropyrimidine based therapy following treatment with CB-839 and capecitabine chemotherapy. Overall survival is defined as the time from randomization to death from any cause.

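### The phase II response-evaluable set in section 12.1 leaves out treated patients who are never re-scanned, which inflates the response rate if any such patients occur

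*Combined protocol and SAP*

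**What the plan says.** Section 12.1 sets out the response-evaluable group as follows: "Only those patients who have measurable disease present at baseline, have received at least one cycle of therapy, and have had their disease re-evaluated". Those patients are then classified by RECIST. A note adds one exception: "Patients who exhibit objective disease progression prior to the end of cycle 1 will also be considered evaluable". Death, clinical deterioration, withdrawal and toxicity without a scan are not mentioned. The toxicity set in the same section, by contrast, takes every patient with at least one dose.

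Section 11.2 schedules the first phase II restaging CT at "Cycle 3, sometime between days 15-21 of treatment cycle".

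A note in section 12.4 deals with "Patients with a global deterioration of health status requiring discontinuation of treatment without objective evidence of disease progression at that time". They are recorded under a separate label, and sites are asked to try to document progression later. The note does not make them non-responders, and the best-response table has no row for a patient who was never re-evaluated.

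Section 14.1.2 lists as a secondary endpoint "Phase II: Response rate as assessed by RECIST criteria of combination CB-839 and capecitabine chemotherapy". Section 14.3 describes a response analysis for phase I only. The intent-to-treat population named in 14.4 serves the correlative studies.

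Two other provisions bear on the point. Section 4.2.2 requires measurable disease at phase II entry. Section 3.3.2 replaces a phase II patient who takes less than 75% of the planned doses of each drug before the nine-week assessment: "the patient will be replaced because he/she has not taken enough drug to assess efficacy".

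**The concern.** The rule treats early failures unequally. Progression seen on a scan stays in the denominator. A death, a clinical decline or a toxicity stop with no scan leaves it, although that patient was treated and did not respond. The denominator then depends on surviving and staying on study long enough to be imaged, up to about nine weeks if no earlier scan is done. A toxicity stop counts in the safety analysis but can vanish from the efficacy estimate.

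This is a single-arm trial of at most 40 phase II patients, with no control group subject to the same selection. A response rate from the 12.1 set would be compared with outside experience, and part of its apparent activity could come from who was left out. Because every eligible phase II patient has measurable disease, the measurability condition gives no reason to exclude any of them.

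**Working it through.** **The plan's own figures.** The documents state no expected response rate and no expected unscanned share, so this endpoint has no figure to reproduce. I borrow only N = 40 (18 + 22) from section 14.2, where it supports the 6-month progression-free rate (18% against 36%). An exact one-sided binomial calculation, with the stage 1 rule as written (stop if fewer than 3 of 18) and an assumed final cut-off of at least 12 of 40 (none is stated), gives type I error 0.044 and power 0.826. So 40 is a workable total. The early-stopping probability of 0.589 fits stopping at 3 or fewer of 18; the rule as written gives 0.346. That is a separate matter and does not enter here.

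**Direction.** Let N be the number treated, u the number never re-evaluated, x the number of responders and d = u/N.

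- All-treated rate: x/N.
- Rate on the 12.1 set: x/(N - u).
- Ratio: N/(N - u) = 1/(1 - d).

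An unscanned patient cannot be in x, so the ratio is 1 when u = 0 and above 1 otherwise.

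**Size.** N = 40 treated, no replacement, x = 4 (assumed, for illustration), u assumed:

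| Unscanned u | d | Factor 1/(1-d) | 12.1 set | All treated |
|---|---|---|---|---|
| 2 | 5% | 1.053 | 4/38 = 10.5% | 4/40 = 10.0% |
| 4 | 10% | 1.111 | 4/36 = 11.1% | 10.0% |
| 6 | 15% | 1.176 | 4/34 = 11.8% | 10.0% |
| 8 | 20% | 1.25 | 4/32 = 12.5% | 10.0% |
| 10 | 25% | 1.333 | 4/30 = 13.3% | 10.0% |

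**If the lost patients are replaced.** Suppose all six unscanned patients are replaced and every replacement is scanned. Then 46 are treated and 40 are evaluable. Four responders give 4/40 = 10.0% on the 12.1 set and 4/46 = 8.7% on all treated. The factor is 46/40 = 1.15 = 1/(1 - 6/46). Replacement restores the sample size but does not remove the inflation.

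**Disease control.** If a disease control rate were computed on the 12.1 set, the same factor would apply: 20 patients with control give 20/34 = 58.8% instead of 20/40 = 50.0%, or 20/36 = 55.6% with four unscanned. The documents do not say that it is computed on that set.

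**Overlap with 3.3.2.** Take planned doses as the full nine weeks and assume complete adherence.

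- CB-839: 63 days x 2 = 126 doses; 75% is 94.5, so the 95th dose, on day 48.
- Capecitabine: 42 dosing days x 2 = 84 doses; 75% is 63. Two cycles supply 56, and the seventh further dose falls on cycle 3 day 4, which is study day 46.
- First CT: cycle 3 days 15-21, which is study days 57-63.

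A fully adherent patient lost unscanned between day 48 and the CT is not replaced under 3.3.2, yet 12.1 still drops that patient.

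**The case against.** **The denominator is inferred.** Section 12.1 says who is evaluable and gets classified; it does not say that the reported phase II rate uses that set. This is correct as far as it goes. But it is the only response set the documents define, and 14.3 offers no phase II alternative. Following the text leads to this denominator.

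**Replacement already removes most of these patients.** On the day counts above, most losses before about week 7 fall under 3.3.2 as well, so 12.1 acts alone on a narrow group. This stands. It limits what 12.1 adds by itself, and it means the fix must reach 3.3.2. The two rules are still not the same, and correcting 3.3.2 alone would leave retained but unscanned patients outside the response set.

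**Unscanned losses are discouraged.** Sections 6.6 and 12.4 ask for effort to complete assessments and document progression, and re-evaluation need not be the scheduled CT. A patient who stops after cycle 1 and is then scanned stays evaluable. This may keep d small; it does nothing for a patient who dies unscanned.

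**The shift is small against the precision.** At 15% unscanned it is 1.8 points, while the exact 95% interval for 4/40 runs from roughly 3% to 24%. That is fair, but the shift can go only one way and costs nothing to avoid.

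**Evaluable-only sets are a familiar convention.** That supports keeping the set as a secondary look, not as the only one defined.

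**A stronger reading.** A reader might infer that 12.1 biases the primary result, since section 12.0 says "Response rate is the primary endpoint for the phase II portion of the trial" and sections 2.1.2 and 14.5 name disease control rate. The decision rule in 14.2, however, is a count out of 18 on 6-month status, in a trial whose sections 14.1.1 and 14.2 make progression-free survival primary and in which death is an event. The 12.1 set plays no part in that rule. If similar selection reaches the primary endpoint, it does so through replacement under 3.3.2.

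**Conclusion.** The concern holds for the phase II response rate, conditionally. As written, treated patients with no post-baseline scan fall outside the only response set defined, unless objective progression was shown before the end of cycle 1. If there are any, the rate is too high by a factor of 1/(1 - d).

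The direction is certain; the size is not. The factor of 1.05 to 1.33 rests on an assumed d of 5-25%, for which the documents give no basis. A reader might take the bias as established, but it is zero if every patient is re-evaluated. Extension to disease control depends on that rate being computed on the 12.1 set, which is not stated. The 6-month progression-free decision rule is not affected by 12.1. The point is worth correcting in the text, but it does not threaten the design.

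**What to change.** For phase II only, state in 12.1 and 14.3 that response rate is computed on all patients who received at least one dose of either drug, including any later replaced under 3.3.2. Count a patient with no post-baseline assessment, for whatever reason, as a non-responder. Keep the present 12.1 set as a labelled supportive analysis, and report the number of patients not re-evaluated with the reason for each.

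Reconcile 3.3.2 with this denominator, so that it is clear a replaced patient still counts in the response rate. Leave the phase I use of 12.1 as it is, because 4.1 does not require measurable disease there.

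The cost is wording in 12.1, 14.3 and 3.3.2. No new data are needed and patient management does not change. The reported response rate may be a few points lower than on the evaluable set.
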